##### **7.1.5.3.2 Safety Follow-up Visit**

The mandatory Safety Follow-up Visit should be conducted approximately 30 days after the last dose of trial treatment or before the initiation of a new antineoplastic treatment, whichever comes first. Subjects with an AE of Grade >1 will be further followed until the resolution of the AE to Grade 0 or 1 or until beginning of a new antineoplastic therapy, whichever occurs first.

Subjects who are eligible for retreatment during the Second Course Phase may have up to 2 Safety Follow-up Visits, the first after the Treatment Phase and the second after the Second Course Phase per the requirements in Section 7.1.5.5 – Second Course Phase.

Imaging assessments should continue as per the interval stated in the protocol; every 9 weeks for the first 54 weeks and then every 12 weeks thereafter. Additional imaging at the Safety Follow-up Visit is not required provided that imaging assessments have been performed per schedule.

#### **7.1.5.4 Follow-up Phase**

All subjects will have post-treatment follow-up for disease status, including initiating a non-study cancer treatment and experiencing disease progression, until death, withdrawing consent, or becoming lost to follow-up.

##### **7.1.5.4.1 Follow-up Visits**

All subjects who discontinue initial trial treatment or Second Course Phase trial treatment for a reason other than disease progression should continue to receive all assessments until PD by RECIST 1.1 or initiation of a new antineoplastic therapy.

Subjects who have received the maximum administrations of pembrolizumab indicated above for either initial treatment or Second Course Phase trial treatment, should be followed as indicated in the Follow-up Phase of the study outlined in Section 6.0 - Trial Flow Chart.

Follow-up Visit 1 should be scheduled to coincide with the next scheduled imaging visit to occur at least 9 weeks after the last dose of trial treatment. Assessment for drug-related AEs, including those consistent with immune phenomena, should occur at Follow-up Visit 1. Follow-up Visit 2 should be scheduled to coincide with the next scheduled imaging visit to occur at least 18 weeks after the last dose of trial treatment. After Follow-up Visit 2, subjects only need to be assessed every 9 weeks ( $63 \pm 7$  days) or 12 weeks ( $84 \pm 7$  days) as defined in Section 7.1.2.6 – Tumor Imaging and Assessments of Disease, by radiologic imaging to monitor disease status, development of drug-related SAEs and ECIs, and initiation of new antineoplastic therapy. Unless otherwise noted in Section 6.0 - Trial Flow Chart, every effort should be made to collect subject information on the start of new antineoplastic therapy, disease progression, and/or death.

Subjects who are eligible to receive retreatment according to the criteria in Section 7.1.5.6 – Second Course Phase will move to the Second Course Phase when they experience disease progression.

##### **7.1.5.4.2 Survival Follow-up**

Once the subject stops the imaging assessments for this protocol (e.g., for PD or starting a new antineoplastic therapy), the subject moves into the Survival Follow-up Phase and should be contacted by telephone every 12 weeks ( $84 \pm 14$  days) to assess for survival status. Survival assessments and its respective entry into the database may be required more frequently around the projected interim or final analyses. Post-study treatments and the subject's response to them will also be collected at the same time.

Survival status data may be requested more frequently than every 12 weeks ( $84 \pm 14$  days) at specific time points during the study. For example, survival status may be requested prior to an external DMC safety review, efficacy IA, and FA. All subjects who are in the Survival Follow-up Phase, and not known to have died prior to the request for this additional survival status time points, will be contacted at that time.

Subjects may withdraw their consent at any time from any or all portions of the study. Subjects who withdraw consent for treatment and/or imaging are encouraged to remain on the noninvasive Survival Follow-up portion of the study. The only procedures associated with this phase are telephone contacts to assess survival status and the current state of the

subject's NSCLC. The noninvasive nature and societal benefit of Survival Follow-up should be explained to the subject by the site staff, particularly when discontinuing treatment and imaging.

#### **7.1.5.5 Survival Status**

To ensure current and complete survival data is available at the time of database locks, updated survival status may be requested during the course of the study by the Sponsor. For example, updated survival status may be requested prior to but not limited to an external Data Monitoring Committee (eDMC) review, IA and/or FA. Upon Sponsor notification, all subjects who do not/will not have a scheduled study visit or study contact during the Sponsor defined time period will be contacted for their survival status (excluding subjects that have a previously recorded death event in the appropriate eCRF).

#### **7.1.5.6 Second Course Phase**

**NOTE: As of Amendment 06, ipilimumab and matching placebo have been removed from the study. This section has been updated accordingly.**

Visit requirements are outlined in Section 6.0 – Trial Flow Chart. Specific procedure-related details are provided above in Section 7.1 – Trial Procedures. Subjects may be eligible to receive up to 17 additional trial treatments of pembrolizumab in the Second Course Phase. After the Second Course Phase, subjects should be followed for progression and survival as indicated, with no option for further retreatment on study.

Subjects will be eligible to receive pembrolizumab at the discretion of the investigator in the Second Course Phase of this study if the subject meets the following conditions:

#### **Either**

- Stopped their initial treatment with pembrolizumab after attaining a confirmed CR according to RECIST 1.1, and
  - Was treated for at least 8 cycles with pembrolizumab
  - Received at least 2 treatments with pembrolizumab beyond the date when the initial CR was declared

#### **OR**

- Had SD, PR, or CR and stopped study treatment after completion of 35 cycles (approximately 2 years) of study treatment for reasons other than disease progression or intolerability

#### **And**

- Experienced radiographic disease progression verified by BICR based on RECIST 1.1 after stopping initial treatment, and:
- Did not receive any anticancer treatment since the last dose of pembrolizumab
- Not more than 2 years have elapsed since discontinuing their initial treatment with pembrolizumab

- The subject meets all of the safety parameters listed in the inclusion criteria and none of the safety parameters listed in the exclusion criteria, and
- The study is ongoing

Subjects will be retreated at the same dose they last received pembrolizumab.

Imaging will be performed every 12 weeks ( $84 \pm 7$  days) after the first dose of Second Course Phase trial treatment until disease progression, or start of new antineoplastic therapy. The timing of imaging should follow calendar days and should not be adjusted for delays in cycle starts or extension of cycle frequencies. The same imaging technique should be used in a subject throughout the trial. Continued imaging is not needed for subjects who start another anticancer treatment regimen. An objective response or disease progression that occurs during the Second Course Phase for a subject will not be counted as an event for the primary analysis of either endpoint in this trial.

#### **7.1.5.7 Discontinued Subjects Continuing to be Monitored in the Trial**

Subjects who discontinue treatment will be followed up for efficacy and OS until consent withdrawal from trial, becoming lost to follow-up, death, or end of the study, whichever comes first.

Date of disease recurrence or metastatic progression, start and stop dates of subsequent anticancer treatments, and reasons for treatments should be recorded in the appropriate eCRF. For subjects who die during the follow up period, the date and cause of death should be recorded in the appropriate eCRF.

### **7.2 Assessing and Recording Adverse Events**

An adverse event is defined as any untoward medical occurrence in a patient or clinical investigation subject administered a pharmaceutical product and which does not necessarily have to have a causal relationship with this treatment. An adverse event can therefore be any unfavourable and unintended sign (including an abnormal laboratory finding, for example), symptom, or disease temporally associated with the use of a medicinal product or protocol-specified procedure, whether or not considered related to the medicinal product or protocol-specified procedure. Any worsening (i.e., any clinically significant adverse change in frequency and/or intensity) of a preexisting condition that is temporally associated with the use of the Sponsor's product, is also an adverse event.

Changes resulting from normal growth and development that do not vary significantly in frequency or severity from expected levels are not to be considered adverse events. Examples of this may include, but are not limited to, teething, typical crying in infants and children and onset of menses or menopause occurring at a physiologically appropriate time.

Sponsor's product includes any pharmaceutical product, biological product, device, diagnostic agent or protocol-specified procedure, whether investigational (including placebo or active comparator medication) or marketed, manufactured by, licensed by, provided by or distributed by the Sponsor for human use.

Adverse events may occur during clinical trials, or as prescribed in clinical practice, from overdose (whether accidental or intentional), from abuse and from withdrawal.

Progression of the cancer under study is not considered an adverse event.

All adverse events that occur after the consent form is signed but before treatment allocation/randomization must be reported by the investigator if they cause the subject to be excluded from the trial, or are the result of a protocol-specified intervention, including but not limited to washout or discontinuation of usual therapy, diet, placebo treatment or a procedure. From the time of treatment allocation/randomization through 30 days following cessation of treatment, all adverse events must be reported by the investigator. Such events will be recorded at each examination on the Adverse Event case report forms/worksheets. The reporting timeframe for adverse events meeting any serious criteria is described in section 7.2.3.1. The investigator will make every attempt to follow all subjects with non-serious adverse events for outcome.

Electronic reporting procedures can be found in the Electronic Data Capture (EDC) data entry guidelines. Paper reporting procedures can be found in the Investigator Trial File Binder (or equivalent).

Adverse events will not be collected for subjects during the pre-screening period (for determination of archival tissue status) as long as that subject has not undergone any protocol-specified procedure or intervention. If the subject requires a blood draw, fresh tumor biopsy etc., the subject is first required to provide consent to the main study and AEs will be captured according to guidelines for standard AE reporting.

### **7.2.1 Definition of an Overdose for This Protocol and Reporting of Overdose to the Sponsor**

**NOTE: As of Amendment 06, ipilimumab and matching placebo have been removed from the study. Subjects who remain on treatment will receive open-label pembrolizumab monotherapy as per protocol. Text related to ipilimumab/matching placebo in this section is no longer applicable and has been removed.**

For purposes of this trial, an overdose will be defined as any dose exceeding the prescribed dose for pembrolizumab as any dose of 1000 mg or exceeding 5 times the protocol-prescribed dose. No specific information is available on the treatment of overdose of pembrolizumab. In the event of overdose, pembrolizumab should be discontinued and the subject should be observed closely for signs of toxicity. Appropriate supportive treatment should be provided if clinically indicated.

If an adverse event(s) is associated with (“results from”) the overdose of Sponsor's product, the adverse event(s) is reported as a serious adverse event, even if no other seriousness criteria are met.

If a dose of Sponsor's product meeting the protocol definition of overdose is taken without any associated clinical symptoms or abnormal laboratory results, the overdose is reported as a non-serious Event of Clinical Interest (ECI), using the terminology “accidental or intentional overdose without adverse effect.”

All reports of overdose with and without an adverse event must be reported by the investigator within 24 hours to the Sponsor either by electronic media or paper. Electronic reporting procedures can be found in the EDC data entry guidelines. Paper reporting procedures can be found in the Investigator Trial File Binder (or equivalent).

## **7.2.2 Reporting of Pregnancy and Lactation to the Sponsor**

Although pregnancy and lactation are not considered adverse events, it is the responsibility of investigators or their designees to report any pregnancy or lactation in a subject (spontaneously reported to them) that occurs during the trial.

Pregnancies and lactations that occur after the consent form is signed but before treatment allocation/randomization must be reported by the investigator if they cause the subject to be excluded from the trial, or are the result of a protocol-specified intervention, including but not limited to washout or discontinuation of usual therapy, diet, placebo treatment or a procedure. Pregnancies and lactations that occur from the time of treatment allocation/randomization through 120 days following cessation of Sponsor's product, or 30 days following cessation of trial treatment if the subject initiates new anticancer therapy, whichever is earlier, must be reported by the investigator. All reported pregnancies must be followed to the completion/termination of the pregnancy. Pregnancy outcomes of spontaneous abortion, missed abortion, benign hydatidiform mole, blighted ovum, fetal death, intrauterine death, miscarriage and stillbirth must be reported as serious events (Important Medical Events). If the pregnancy continues to term, the outcome (health of infant) must also be reported.

Such events must be reported within 24 hours to the Sponsor either by electronic media or paper. Electronic reporting procedures can be found in the EDC data entry guidelines. Paper reporting procedures can be found in the Investigator Trial File Binder (or equivalent).

## **7.2.3 Immediate Reporting of Adverse Events to the Sponsor**

### **7.2.3.1 Serious Adverse Events**

A serious adverse event is any adverse event occurring at any dose or during any use of Sponsor's product that:

- Results in death;
- Is life threatening;
- Results in persistent or significant disability/incapacity;
- Results in or prolongs an existing inpatient hospitalization;
- Is a congenital anomaly/birth defect;
- Is an other important medical event.

**Note:** In addition to the above criteria, adverse events meeting either of the below criteria, although not serious per ICH definition, are reportable to the Sponsor in the same timeframe as SAEs to meet certain local requirements. Therefore, these events are considered serious by the Sponsor for collection purposes.

- Is a new cancer (that is not a condition of the study);
- Is associated with an overdose.

Refer to [Table 10](#) for additional details regarding each of the above criteria.

For the time period beginning when the consent form is signed until treatment allocation/randomization, any serious adverse event, or follow up to a serious adverse event, including death due to any cause other than progression of the cancer under study (reference

Section 7.2.3.3 for additional details), that occurs to any subject must be reported within 24 hours to the Sponsor if it causes the subject to be excluded from the trial, or is the result of a protocol-specified intervention, including but not limited to washout or discontinuation of usual therapy, diet, placebo treatment or a procedure.

For the time period beginning at treatment allocation/randomization through 90 days following cessation of trial treatment, or 30 days following cessation of trial treatment if the subject initiates new anticancer therapy, whichever is earlier, any serious adverse event, or follow up to a serious adverse event, including death due to any cause other than progression of the cancer under study (reference Section 7.2.3.3 for additional details), whether or not related to the Sponsor's product, must be reported within 24 hours to the Sponsor either by electronic media or paper. Electronic reporting procedures can be found in the EDC data entry guidelines. Paper reporting procedures can be found in the Investigator Trial File Binder (or equivalent).

Additionally, any serious adverse event, considered by an investigator who is a qualified physician to be related to the Sponsor's product that is brought to the attention of the investigator at any time following consent through the end of the specified safety follow-up period specified in the paragraph above, or at any time outside of the time period specified in the previous paragraph also must be reported immediately to the Sponsor.

All subjects with serious adverse events must be followed up for outcome.

### **7.2.3.2 Events of Clinical Interest**

Selected non-serious and serious adverse events are also known as Events of Clinical Interest (ECI) and must be reported to the Sponsor.

For the time period beginning when the consent form is signed until treatment allocation/randomization, any ECI, or follow up to an ECI, that occurs to any subject must be reported within 24 hours to the Sponsor if it causes the subject to be excluded from the trial, or is the result of a protocol-specified intervention, including but not limited to washout or discontinuation of usual therapy, diet, placebo treatment or a procedure.

For the time period beginning at treatment allocation/randomization through 30 days following cessation of treatment, any ECI, or follow up to an ECI, whether or not related to the Sponsor's product, must be reported within 24 hours to the Sponsor, either by electronic media or paper. Electronic reporting procedures can be found in the EDC data entry guidelines. Paper reporting procedures can be found in the Investigator Trial File Binder (or equivalent).

Events of clinical interest for this trial include:

1. an overdose of Sponsor's product, as defined in Section 7.2.1 - Definition of an Overdose for This Protocol and Reporting of Overdose to the Sponsor, that is not associated with clinical symptoms or abnormal laboratory results.
2. an elevated AST or ALT lab value that is greater than or equal to 3X the upper limit of normal and an elevated total bilirubin lab value that is greater than or equal to 2X the upper limit of normal and, at the same time, an alkaline phosphatase lab value that is less than 2X the upper limit of normal, as determined by way of protocol-specified laboratory testing or unscheduled laboratory testing.\*

\*Note: These criteria are based upon available regulatory guidance documents. The purpose of the criteria is to specify a threshold of abnormal hepatic tests that may require an additional evaluation for an underlying etiology. The trial site guidance for assessment and follow up of these criteria can be found in the Investigator Trial File Binder (or equivalent).

### **7.2.3.3 Protocol-Specific Exceptions to Serious Adverse Event Reporting**

Efficacy endpoints as outlined in this section will not be reported to the Sponsor as described in Section 7.2.3 – Immediate Reporting of Adverse Events to the Sponsor.

Specifically, the suspected/actual events covered in this exception include any event that is disease progression of the cancer under study.

The Sponsor will monitor unblinded aggregated efficacy endpoint events and safety data to ensure the safety of the subjects in the trial. Any suspected endpoint which upon review is not progression of the cancer under study will be forwarded to Global Safety as a SAE within 24 hours of determination that the event is not progression of the cancer under study.

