## 8.2 Responsibility for Analyses/In-House Blinding

**Note: As of Amendment 06, the study will be unblinded to the Sponsor, the investigational sites, and the participants.**

The statistical analysis of the data obtained from this study will be the responsibility of the Clinical Biostatistics department of the Sponsor.

This study will be conducted as a double-blinded study under in-house blinding procedures. The official, final database will not be unblinded until medical/scientific review has been performed, protocol deviations have been identified, and data have been declared final and complete.

The Sponsor will generate the randomized allocation schedule(s) for study treatment assignment for this protocol, and the randomization will be implemented in an IVRS/IWRS.

Planned interim analyses are described in Section 8.7 – Interim Analyses. Blinding to treatment assignment will be maintained at all investigational sites. Treatment-level results of the planned interim analyses will be provided by the external unblinded statistician to the DMC. Limited additional Sponsor personnel may be unblinded to the treatment level results of the interim analyses, if required, in order to act on the recommendations of the DMC (e.g., interaction with regulatory agencies). The extent to which individuals are unblinded with respect to results of interim analyses will be documented by the unblinded statistician.

The DMC will serve as the primary reviewer of the results of the interim analyses and will make recommendations for discontinuation of the study or modification to an EOC of the Sponsor. Depending on the recommendation of the DMC, the Sponsor may prepare a regulatory submission. If the DMC recommends modifications to the design of the protocol or discontinuation of the study, this EOC and limited additional Sponsor personnel may be unblinded to results at the treatment level in order to act on these recommendations. The DMC responsibilities, review schedules, and additional logistical details will be provided in the DMC Charter.

Prior to final study unblinding, the external unblinded statistician will not be involved in any discussions regarding modifications to the protocol, statistical methods, identification of protocol deviations, or data validation efforts after the interim analyses.

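### Does the Sponsor's monitoring of unblinded aggregated efficacy events in Section 7.2.3.3 undermine the in-house blinding in Section 8.2?

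*Combined protocol and SAP*

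**What the plan says.** Section 7.2.3.3 exempts progression of the cancer under study from expedited SAE reporting. It then adds a safeguard: "The Sponsor will monitor unblinded aggregated efficacy endpoint events and safety data to ensure the safety of the subjects in the trial". The sentence after it sends any suspected endpoint that proves not to be progression to the Sponsor's safety group as an SAE within 24 hours.

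Section 8.2 covers responsibility for the analysis and blinding:

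- On the general rule: "This study will be conducted as a double-blinded study under in-house blinding procedures".
- On interim results: "Treatment-level results of the planned interim analyses will be provided by the external unblinded statistician to the DMC".
- On the exception for the Sponsor: "Limited additional Sponsor personnel may be unblinded to the treatment level results of the interim analyses, if required". The purpose given is acting on what the DMC recommends.
- On the record of access: "The extent to which individuals are unblinded with respect to results of interim analyses will be documented by the unblinded statistician".
- On the present state, in a note at its head: "As of Amendment 06, the study will be unblinded to the Sponsor, the investigational sites, and the participants".

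Sections 7.2.7 and 8.8.4 make the DMC responsible for judging overall risk and benefit, and let it ask for efficacy data when a safety concern arises. Section 7.2.7 presents the DMC as an addition to routine trial monitoring.

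**The concern.** The two sections appear to give different answers on who could see unblinded efficacy data. Ongoing safety monitoring by the Sponsor is not the exception that Section 8.2 allows, which is limited to interim results and to acting on DMC recommendations. Sections 5.2.3, 7.1.4.2 and 8.2 each received an Amendment 06 note on blinding. Section 7.2.3.3 did not, so nothing in its text confines it to the open-label period.

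The credibility of the choices made before IA1 would be at stake. Section 8.6.1 requires strata to be pooled on a blinded review of counts, and Section 8.6.1.5 requires the PRO time point to be chosen on blinded data. The Sponsor's biostatistics department is responsible for the analysis. If that department had seen efficacy events by arm, neither choice could be called blinded. Because Section 10.7 says the protocol and SAP go with the manuscript, a journal reviewer would read both statements.

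**Working it through.** There is no figure to reproduce: the point involves no alpha, power, event count or sample size. The check is a comparison of texts.

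**Step 1. When is there a conflict?** Two things are left open in Section 7.2.3.3: the period, and whether aggregated data means data pooled over arms or summarised by arm.

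| | Pooled over arms | Summarised by arm |
|---|---|---|
| Before Amendment 06 | No conflict: no treatment comparison is revealed | Conflict with Section 8.2 |
| From Amendment 06 | No conflict | No conflict: the Sponsor is unblinded |

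Only one of the four cells is inconsistent. The by-arm reading is the more natural one, since pooled data are not usually called unblinded, but the text does not settle it.

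**Step 2. Did the sentence apply in the blinded phase?** Probably. The Amendment 06 table of changes does not list Section 7.2.3.3. Its entry for changes throughout the document covers removed references to ipilimumab and placebo and minor edits, and a new Sponsor monitoring role would hardly count as minor. This is inference, because the earlier protocol is not among the documents. The cross-reference from Section 7.2.3.1, which covers SAEs "For the time period beginning at treatment allocation/randomization through 90 days following cessation of trial treatment", does not help: it points to Section 7.2.3.3 for the exclusion of progression deaths, not for the monitoring sentence.

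**Step 3. Is any other section contradicted?** No. Since Section 7.2.7 places the DMC on top of routine monitoring, some Sponsor safety monitoring beside it is expected. Giving the DMC the risk and benefit judgement does not exclude it. The tension is with Section 8.2 alone.

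**Step 4. Does the firewall on the external statistician strengthen the point?** Only weakly. Section 8.2 says "the external unblinded statistician will not be involved in any discussions regarding modifications to the protocol, statistical methods", but that sentence ends by tying the restriction to the time after the interim analyses. Pooling was to be fixed before the database lock for the first analysis of each endpoint, so the restriction may not reach that decision.

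**Step 5. What would change today?**

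- Section 8.7.2 sets the IA1 trigger by deaths and time since the last randomization, not by any observed treatment difference.
- Pooling and the PRO time point carry their own blinded-review requirements, whatever Section 7.2.3.3 says.
- The opening note of Section 8.0 records that IA1 met the success criteria for neither PFS nor OS, that a nonbinding futility analysis requested by the eDMC met its criteria, and that no further prespecified analysis of primary or secondary endpoints will follow.
- Under Sections 8.1 and 8.8.1, ORR can be tested only after a rejection on the primary endpoints, so it is not tested either.

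No positive efficacy claim remains for Sponsor access to have inflated.

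**The case for a change.** The best argument for a change is that it costs little and that the record matters. The sentence very likely stood during the blinded phase. SAP assumptions were updated on 14-FEB-2020, and assumptions and interim timing again on 14-JUL-2020. The second date is 49 days before the IA1 cutoff of 01-SEP-2020 (17 days left in July, 31 in August, 1 in September). When a sponsor revises its analysis plan that close to a cutoff, its blinding status should be beyond doubt. One line in Section 7.2.3.3 and one in the clinical study report would achieve that. The access record required by Section 8.2 covers interim results only and would not capture other access.

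The ambiguity, the likely timing and the limit of that record all stand. What does not stand is the step from there to a needed amendment. Nothing in the documents suggests that data by arm reached the Sponsor outside Section 8.2 or influenced either amendment. A note added now would govern a phase that has ended. It could not establish what access took place; only the Sponsor's own confirmation could do that. A statement on blinding in the study report is ordinary good reporting and does not need a change to the plan. A repeat of the IA1 analyses with all randomization strata unpooled would answer an event for which there is no evidence.

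**Conclusion.** This is a loosely worded safety sentence that does not sit well with the blinding section under one reading of one past period. It is not a fault in the current plan. Under Amendment 06 the sentence is compatible with Section 8.2, and its working purpose, catching events wrongly set aside as progression, is unaffected. For the blinded phase an analyst would take Section 8.2 as governing access to treatment-level data.

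The effect on computed results is nil: no test, boundary, event count or estimate depends on the sentence, and the efficacy analyses that remained have been cancelled. The conclusion assumes that Section 8.2 was followed in practice up to IA1, which the documents neither prove nor call into question. If the Sponsor knows of access outside that route, it belongs in the study report as a matter of conduct. It would still not call for rewriting the plan.
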